### 9.2.2 Visit 1 – Initial Visit (Baseline, Day 1)

1. Obtain written informed consent from the subject as detailed in section 9.1.
2. Obtain demographic information, relevant medical history, and relevant concomitant medications.
3. Screen the subject against protocol inclusion and exclusion criteria.
4. Provide the subject with a copy of the CWIS, and allow sufficient time to complete it. Staff should not assist the subject with the questionnaire, other than to instruct the subject to complete all questions. Ensure that the subject has completed the CWIS questionnaire appropriately, providing a single valid response for each item of the questionnaire.

NOTE: subjects who cannot read/write may have the CWIS read aloud to them and the subject's responses recorded. Ensure this process is noted in the source documents.
5. Complete an ulcer assessment (see Section 9.5.1) including ulcer classification, i.e. pressure ulcer staging or Wagner classification for DFU (see Section 9.5.5).
6. If the reference ulcer is a DFU or LU, determine ABI. Values obtained within the last 30 days may be used to qualify the subject.

Note for DFU subjects: Subjects with a DFU and an ABI value less than 0.7 may not be enrolled.

VLU subjects that will use compression during the study should have an ABI that meets the requirements stated in the IFU for the selected compression device.
7. Assign the subject a study number and allocate the subject to either the ALNB (experimental) or SC (comparator group) according to the randomization schedule provided by SealedEnvelope.

8. Photograph the ulcer. Ensure that the calibration ruler with subject's initials and visit date is visible in the image. If the ulcer is debrided, take a photograph of the ulcer immediately prior to and following debridement. Record any debridement and the method of debridement in the electronic Case Report Form (eCRF).
9. Apply dressing according to randomization:
  - For subjects allocated to the ALNB group, apply ALNB as instructed in Section 6.2.2.
  - For subjects allocated to SC, apply a suitable dressing per dressing IFU.
10. Record details of all dressings used for all subjects, (e.g. brand, size, etc.) as well as any treatment applied underneath the dressing, such as Durafiber or Intrasite gel.
11. Assess the ease of applying the dressing (Section 9.5.7), including remains in place and repositioning (if applicable).

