#### 10.2.2.2 *Secondary*

##### Ulcer progression

Ulcer progression variables will be summarized by treatment group at three, six, and twelve weeks.

Part of the assessment of ulcer progression will be done using a modified version of the Bates-Jensen Wound Assessment tool with the following variables being assessed (see section 9.5.1 for the scales used):

- Undermining

- Necrotic tissue type
- Necrotic tissue amount
- Exudate type
- Exudate amount
- Skin color surrounding the wound
- Granulation tissue
- Epithelialization

Other assessments of ulcer progression to be summarized include:

- Condition of peri-wound (categorized as Normal, Erythematous, Edematous, Eczematous, Excoriated, Macerated, Indurated) and the condition of peri-wound at each post-baseline time point cross-tabulated with condition of peri-wound at baseline to be summarized separately.
- Ulcer length/width/depth will be used to derive area and volume. These variables will then be used to derive the reduction in area, depth, and volume from baseline to three, six and twelve weeks. The reduction in each dimension at each assessment will be analyzed as the dependent variable in separate linear regression models. An estimate of the difference between treatments in the reduction from baseline area, depth, and volume (separately) will be reported with the corresponding 95% confidence interval.
- Reference ulcer healed (100% re-epithelialized, no drainage, no need for a dressing) will be summarized at each assessment (at three, six, and twelve weeks) and analyzed using separate logistic regression models with whether the reference ulcer was healed or not at the assessment as the dependent variable.

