5.3 Secondary Endpoints

Ulcer progression variables to be compared between groups at three, six, and twelve weeks including:

- Modified Bates-Jensen Wound Assessment Tool
 - Undermining
 - Necrotic tissue type
 - Necrotic tissue amount
 - Exudate type

CONFIDENTIAL AND PROPRIETARY

This document contains information that is confidential and proprietary to Smith & Nephew PLC and Smith & Nephew, Inc. and is intended for use only by Smith & Nephew and its manufacturer. It shall not be reproduced or copied in whole or in part, nor shall the contents be disclosed by any means without prior written permission from Smith & Nephew, nor shall anyone make any use of it that is contrary to the expressed or implied wishes of Smith & Nephew

Statistical Analysis Plan	
A Pilot Randomized Controlled Trial to Evaluate an Advanced Borderless Dressing (ALLEVYN™ LIFE Non-Bordered) in the Treatment of Chronic Ulcers	Number: CT1603ALF
	ST: 1005
	Version: 1.0, 27-Jul-2018
	Page: 11 of 27

- Exudate amount
- Skin color surrounding the wound
- Granulation tissue
- Epithelialization
- Condition of peri-wound
- Ulcer dimensions
- Ulcer healed status

Healthcare resource use variables (to be compared between groups over the entire twelve week study period) including:

- Dressings used (number and type for both primary and secondary dressings), including use of compression therapy
- Healthcare consultations (number and type)
- Time spent by health care providers (HCP) in treating/caring for reference ulcer
- Time in hospital (nights spent as an inpatient due to reference ulcer)
- Interventions/procedures related to the reference ulcer (number and type), including debridement of the ulcer (curette, scissors, scalpel, forceps, other)
- Concomitant therapies/treatments (number and type) used on the reference ulcer

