If the data meets the assumptions of using ANCOVA then as a secondary analysis a repeated measures ANCOVA model will be used, with the CWIS-PSDL score as the dependent variable. As a minimum the model will contain terms for treatment, visit and treatment-by-visit interaction. The following terms will be added to the model using a stepwise selection procedure with an F-value to attain a significance level of 0.1: centre, wound type, BMI and baseline CWIS-PSDL score.. P-values for the type III effects in the model will be presented.

Sensitivity Analysis

If LOCF methods are used to account for any missing CWIS-PSDL data at 6 weeks then a sensitivity analysis the same as the primary analysis (ANCOVA model) described above will be carried out on the data treating all missing data as missing with no imputation.

The primary endpoint analysis will be repeated using the per-protocol population (with and without the LOCF imputation).

CONFIDENTIAL AND PROPRIETARY

This document contains information that is confidential and proprietary to Smith & Nephew PLC and Smith & Nephew, Inc. and is intended for use only by Smith & Nephew and its manufacturer. It shall not be reproduced or copied in whole or in part, nor shall the contents be disclosed by any means without prior written permission from Smith & Nephew, nor shall anyone make any use of it that is contrary to the expressed or implied wishes of Smith & Nephew

Statistical Analysis Plan	
A Pilot Randomized Controlled Trial to Evaluate an Advanced Borderless Dressing (ALLEVYN™ LIFE Non-Bordered) in the Treatment of Chronic Ulcers	Number: CT1603ALF
	ST: 1005
	Version: 1.0, 27-Jul-2018
	Page: 22 of 27

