7.11 Analysis of Secondary Endpoints

Modified Bates- Jensen Wound Assessment Tool

Part of the assessment of ulcer progression will be done using a modified version of the Bates- Jensen Wound Assessment tool assessing: undermining, necrotic tissue type, necrotic tissue amount, exudate type, exudate amount, skin color surrounding the wound, granulation tissue and epithelialization. Each item will be scored according to section 9.5.1 of the study protocol. A total score for each subject at each assessment will be calculated by summing the scores for all 8 items.

The total score for the modified Bates- Jensen Wound Assessment tool will be summarized using descriptive statistics at all visits by treatment and overall. Repeated measures ANCOVA model will be used with the total score as the dependent variable. As a minimum the model will contain terms for treatment, visit and a treatment-by-visit interaction term. The following terms will be added to the model using a stepwise selection procedure with an F-value to attain a significance level of 0.1: centre, wound

CONFIDENTIAL AND PROPRIETARY

This document contains information that is confidential and proprietary to Smith & Nephew PLC and Smith & Nephew, Inc. and is intended for use only by Smith & Nephew and its manufacturer. It shall not be reproduced or copied in whole or in part, nor shall the contents be disclosed by any means without prior written permission from Smith & Nephew, nor shall anyone make any use of it that is contrary to the expressed or implied wishes of Smith & Nephew

Statistical Analysis Plan	
A Pilot Randomized Controlled Trial to Evaluate an Advanced Borderless Dressing (ALLEVYN™ LIFE Non-Bordered) in the Treatment of Chronic Ulcers	Number: CT1603ALF
	ST: 1005
	Version: 1.0, 27-Jul-2018
	Page: 23 of 27

type, BMI and baseline CWIS-PSDL score. The difference in least squares mean (LSMean) between treatments at the 3, 6 and 12 week visit will be presented with the associated 95% confidence interval.

Other assessments of ulcer progression

- Condition of peri-wound (categorized as Normal, Erythematous, Edematous, Eczematous, Excoriated, Macerated, Indurated) at each post-baseline time point cross-tabulated with condition of peri-wound at baseline.

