- Ulcer length/width/depth will be used to derive area and volume. These variables will then be used to derive the reduction in area, depth, and volume from baseline to three, six and twelve weeks. The reduction in each dimension at each assessment (3, 6 and 12 weeks) will be analysed as the dependent variable in separate ANCOVA models. As a minimum the models will contain a term for treatment. The following terms will be added to the model using a stepwise selection procedure with an F-value to attain a significance level of 0.1: centre, subject, wound type, BMI and the relevant baseline wound dimension (area/ depth/ volume). The estimate difference in the LSMean reductions from baseline in area, depth, and volume (separately) between treatments will be presented with the associated 95% confidence interval.
- Reference ulcer healed (100% re-epithelialized, no drainage, no need for a dressing) will be summarized at each assessment (at three, six, and twelve weeks) and analyzed using a repeated measures logistic regression model with whether the reference ulcer was healed or not at the assessment as the dependent variable. As a minimum the model will contain a term for treatment. The following terms will be added to the model using a stepwise selection procedure with an F-value to attain a significance level of 0.1: centre, wound type and BMI..

Healthcare resource use

CONFIDENTIAL AND PROPRIETARY

This document contains information that is confidential and proprietary to Smith & Nephew PLC and Smith & Nephew, Inc. and is intended for use only by Smith & Nephew and its manufacturer. It shall not be reproduced or copied in whole or in part, nor shall the contents be disclosed by any means without prior written permission from Smith & Nephew, nor shall anyone make any use of it that is contrary to the expressed or implied wishes of Smith & Nephew

Statistical Analysis Plan	
A Pilot Randomized Controlled Trial to Evaluate an Advanced Borderless Dressing (ALLEVYN™ LIFE Non-Bordered) in the Treatment of Chronic Ulcers	Number: CT1603ALF
	ST: 1005
	Version: 1.0, 27-Jul-2018
	Page: 24 of 27

The following Healthcare resource variables will be summarized by treatment groups and overall (i.e. all assessments together) using continuous or categorical data summaries (as appropriate):

- Number and type of dressings used (both primary and secondary dressings), including use of compression therapy
- Number of outpatient visits

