7.15 Changes in Analysis Methods Specified in the Protocol

The following changes were made to the methods specified in the protocol:

- For the Modified Bates- Jensen Wound Assessment Tool, instead of using a t-test to test for a difference between treatments in the total score at 12 weeks, the repeated measures ANOVA model which was already being used will also be used to

CONFIDENTIAL AND PROPRIETARY

This document contains information that is confidential and proprietary to Smith & Nephew PLC and Smith & Nephew, Inc. and is intended for use only by Smith & Nephew and its manufacturer. It shall not be reproduced or copied in whole or in part, nor shall the contents be disclosed by any means without prior written permission from Smith & Nephew, nor shall anyone make any use of it that is contrary to the expressed or implied wishes of Smith & Nephew

Statistical Analysis Plan	 smith&nephew
A Pilot Randomized Controlled Trial to Evaluate an Advanced Borderless Dressing (ALLEVYN™ LIFE Non-Bordered) in the Treatment of Chronic Ulcers	Number: CT1603ALF
	ST: 1005
	Version: 1.0, 27-Jul-2018
	Page: 27 of 27

estimate the difference in least squares mean (LSMean) between treatments at the 12 week visit along with associated 95% confidence interval.

- The number of serious device-related adverse events is expected to be low, so it would not be useful to calculate the 1-sided upper 95% CI as originally planned in the protocol. Instead the number will be summarised and the individual cases will be listed.

CONFIDENTIAL AND PROPRIETARY

This document contains information that is confidential and proprietary to Smith & Nephew PLC and Smith & Nephew, Inc. and is intended for use only by Smith & Nephew and its manufacturer. It shall not be reproduced or copied in whole or in part, nor shall the contents be disclosed by any means without prior written permission from Smith & Nephew, nor shall anyone make any use of it that is contrary to the expressed or implied wishes of Smith & Nephew

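### Three secondary ulcer models in SAP 7.11 are mis-specified: the Bates-Jensen model omits its own baseline, the repeated-measures healing model has no visit term, and the dimension models offer subject as a term with one record each

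*SAP*

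**What the plan says.** **Bates-Jensen.** SAP 7.11 fits a repeated-measures ANCOVA to the total score itself, not to its change. Treatment, visit and their interaction are forced. Stepwise candidates at the 0.1 level are centre, wound "type, BMI and baseline CWIS-PSDL score. The difference in least squares mean (LSMean) between treatments at the 3, 6 and 12 week visit" is then to be presented with a 95% interval. The same candidate list appears in SAP 7.9 for the CWIS-PSDL repeated-measures model. Protocol 9.2.2, step 5, collects the items at Visit 1: "Complete an ulcer assessment (see Section 9.5.1) including ulcer classification, i.e. pressure ulcer staging or Wagner classification for DFU".

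**Healing.** SAP 7.11 has healed status "analyzed using a repeated measures logistic regression model with whether the reference ulcer was healed or not at the assessment as the dependent variable". Treatment is the only forced term, and the candidates are centre, wound type and BMI. Protocol 10.2.2.2 had it "analyzed using separate logistic regression models with whether the reference ulcer was healed or not at the assessment as the dependent variable". SAP 5.3 introduces the endpoint with "Ulcer progression variables to be compared between groups at three, six, and twelve weeks including". SAP 7.15 opens with "The following changes were made to the methods specified in the protocol" and lists two items, one on the Bates-Jensen comparison and one on the confidence limit for serious device-related events. The healing model is not among them.

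**Dimensions.** SAP 7.11 fits a separate ANCOVA for each dimension at each visit, with candidates "centre, subject, wound type, BMI and the relevant baseline wound dimension (area/ depth/ volume").

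**The concern.** Each model departs from what its own outcome or data layout needs.

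- **Bates-Jensen.** The only baseline score on offer belongs to a different instrument. The dimension models in the same section do offer their own baseline, so the SAP itself accepts that kind of adjustment. The list looks carried over from SAP 7.9. At stake is precision, and protection against chance baseline imbalance at 25 vs 15.
- **Healing.** Separate per-visit models need no visit term; a single model across visits does. For the CWIS-PSDL model, SAP 7.9 says "As a minimum the model will contain terms for treatment, visit and treatment-by-visit interaction", and the Bates-Jensen model has the same terms. The healing model has neither visit nor the interaction, so the comparison at each visit gets no treatment estimate with a confidence interval.
- **Dimensions.** With one record per subject, a subject term cannot be estimated. A programmer would have to settle this without guidance.

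The trial exists to supply estimates for planning later work (protocol 5 and 8.2), so the form of these estimates matters even in a pilot.

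**Working it through.** **Inputs from the documents.** 25 ALNB subjects at 5:3 (protocol 11, SAP 6.1): 25 × 8/5 = 40 in total, so 15 on SC, as the plan states. Two-sided 5% level (SAP 7.1). The documents give no standard deviation, correlation or healing rate, so those below are assumptions, shown as ranges.

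**1. Bates-Jensen: cost of omitting the own baseline.** With baseline-to-visit correlation r, adjustment multiplies the residual variance by 1 − r². The unadjusted interval is therefore wider by 1/√(1 − r²). The simulation column uses 4,000 trials per r at 25 vs 15 with t-based intervals, so it charges the extra degree of freedom.

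| r (assumed) | Formula ratio | Simulated half-width without / with baseline (SD) | Simulated ratio |
|---|---|---|---|
| 0.3 | 1.05 | 0.656 / 0.634 | 1.03 |
| 0.5 | 1.15 | 0.657 / 0.576 | 1.14 |
| 0.7 | 1.40 | 0.655 / 0.474 | 1.38 |

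Mean bias was below 0.01 SD. In a single trial, though, a baseline imbalance of one standard error, √(1/25 + 1/15) = 0.327 SD, shifts the unadjusted estimate by r × 0.327 = 0.10, 0.16 or 0.23 SD.

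The SAP does not say whether Visit 1 is a response level in this model. If it is, little changes: with an unconstrained treatment-by-visit term and complete data, each visit's difference is still not adjusted for baseline.

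**2. Healing: what a model without visit estimates.** It fits one healing probability per arm for all three visits. Under an independence working model this is the average over visits, and the odds ratio is that of the two averages.

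| Assumed healing at weeks 3/6/12, ALNB vs SC | Odds ratio by visit | Averages | Pooled odds ratio |
|---|---|---|---|
| 5/25/50% vs 5/15/30% | 1.0, 1.9, 2.3 | 26.7% vs 16.7% | 1.82 |
| 10/25/45% vs 5/15/30% | 2.1, 1.9, 1.9 | 26.7% vs 16.7% | 1.82 |

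Here 1.82 = (0.267/0.733)/(0.167/0.833). A treatment-only GEE on 16,000 simulated subjects gave 1.87 and 1.81. Pooling also attenuates: with SC healing of 5/15/35% and a true odds ratio of 2 at every visit, the pooled value is 1.83.

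**3. Healing: can visit-specific estimates be had at 25 vs 15?** The chance that at least one arm has no healed ulcer is 1 − [1 − (1 − pA)²⁵][1 − (1 − pB)¹⁵]:

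- week 3, 5% vs 5%: 61%; 10% vs 5%: 50%
- week 6, 25% vs 15%: 9%
- week 12, 50% vs 30%: 0.5%

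So an ordinary odds ratio will often fail at week 3. A risk difference with a Newcombe 95% interval does not:

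- 1/25 vs 0/15: 4.0 points (−16.7 to 19.5)
- 12/25 vs 4/15: 21.3 points (−9.7 to 45.6)

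**4. Dimensions: the subject term.** With 40 records from 40 subjects, the design of intercept, treatment and subject indicators has rank 40. Residual degrees of freedom are 40 − 40 = 0, against 38 for treatment alone, and treatment has none left after subject. As a random effect, subject is confounded with the residual.

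**The case against.** The strongest reply is that three unequal points are bundled, all on secondary endpoints of a pilot sized on feasibility.

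- **Bates-Jensen.** The loss depends wholly on an assumed correlation and is negligible at the low end. Centre and wound type, as well as CWIS-PSDL, might recover some of it. This stands: the ratios are upper bounds if any selected term does so. Adding the baseline to the candidate list would also cure the omission as text, although a stepwise rule could then drop it.
- **Healing.** Healed status will be summarised at each visit, "compared" need not mean a modelled interval, and the stated minimum is only a floor. The equal 1.82 values are built in, since both ALNB patterns sum to 80% over the visits. At 25 vs 15 the pooled log odds ratio has a simulated standard error of about 0.7, so this trial could not tell the two patterns apart. The last two points are correct. They do not rescue the text: the terms that may be added are listed without visit, and summarised proportions carry no treatment estimate or interval. The example shows what the model targets, not what this sample could detect.
- **Remedy.** An unadjusted risk difference drops wound type, the stratification factor. That is fair, and is why a model-based odds ratio should accompany it where counts allow.
- **Dimensions.** Subject can never validly enter, and the other terms remain usable. This is near-clerical.

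**Conclusion.** The concern holds in all three parts and should be fixed.

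- **Healing** is the most consequential part. As written, the SAP gives no treatment estimate with an interval at any of the three visits it names, and the switch from per-visit models is unrecorded. The illustrative odds ratios rest on assumed healing rates; the missing terms do not.
- **Bates-Jensen** is avoidable imprecision without systematic bias: an interval up to 1.05, 1.15 or 1.40 times wider by formula at assumed correlations of 0.3, 0.5 or 0.7.
- **Subject** in the dimension models is a drafting error. The term cannot be fitted, but the planned estimates survive once it is ignored.

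The primary CWIS-PSDL analysis is not affected.

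**What to change.** In SAP 7.11:

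1. **Bates-Jensen.** Replace baseline CWIS-PSDL with the baseline modified Bates-Jensen total, as a forced covariate. It costs one degree of freedom, already counted in the simulated ratios.
2. **Healing.** At weeks 3, 6 and 12, report the number healed per arm and the ALNB − SC risk difference with a Newcombe or exact 95% interval. Where counts allow, add an odds ratio, either from a model with visit and treatment-by-visit or from the protocol's per-visit models, using a Firth-penalised or exact method. Record the change in SAP 7.15.
3. **Dimensions.** Delete subject from the candidates. The relevant baseline dimension is already offered.

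All variables are already collected, so the cost is SAP wording. The downside is that visit-specific healing intervals will be wide, about 36 points (19.5 + 16.7) and 55 points (45.6 + 9.7) in the two examples, and a week-3 odds ratio will often not be estimable without a penalised or exact method.
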